8.3 Recording Adverse Events

The following subsections detail what information must be documented for each adverse event occurring during the time period specified in Section 8.2 Safety Assessment and Follow-Up.

8.3.1 Relationship to Study Intervention

The relationship to study intervention or study participation must be assessed and documented for all adverse events. Evaluation of relatedness must consider etiologies such as natural history of the underlying disease, concurrent illness, concomitant therapy, study-related procedures, accidents, and other external factors.

The following guidelines are used to assess relationship of an event to study intervention:

1. Related (Possible, Probable, Definite)
 - a. The event is known to occur with the study intervention.
 - b. There is a temporal relationship between the intervention and event onset.
 - c. The event abates when the intervention is discontinued.
 - d. The event reappears upon a re-challenge with the intervention.
2. Not Related (Unlikely, Not Related)
 - a. There is no temporal relationship between the intervention and event onset.
 - b. An alternate etiology has been established.

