The use of an intravenous needle and the fluids given through the needle may cause minor discomfort, bleeding under the skin (bruise), fainting, and possible infection at the site of needle insertion. These risks are minimized by having nursing staff trained in placing IV lines perform these procedures in a safe, aseptic manner. The subjects' alternative is not to participate in this study and have only their scheduled clinical procedure(s) performed.

The invasive pressure measurement procedure (with 18G needle) has low risk similar to a stereotactic breast biopsy (mostly with 14G or larger needles). The risks includes: bruising and swelling of the breast, infection of the measurement site, and soreness at the needle injection. Also, there is low risk of infection and pain and they could be minimized by strict sterile technique and local lidocaine infiltration, respectively. The subjects' alternative is not to participate in the study.

1.4.2 **Benefits**

We do not expect any direct benefit for subjects enrolled in this study. The long-term benefits of this study will be the development of a noninvasive, safe, accurate IFP estimator. Additionally, it may lead to a novel functional predictor of malignancy in breast tumors.

2 **Study Objectives**

2.1 **Objectives**

This study is designed to compare the direct measurements of IFP in the breast tumor and its surrounding tissue with the values obtained from 3D SHAPE data (i.e., CEUS data).

2.1.1 **Primary**

The primary objective of the study is to determine if the 3D SHAPE results can be used to estimate IFPs in breast tumor and its surrounding tissue.

2.1.2 **Secondary**

The secondary objective of the study is to determine if the malignancy of breast tumor can be predicted by the 3D SHAPE results.

2.2 **Endpoints/Outcome Measures**

2.2.1 **Primary**

A Pearson's correlation coefficient above 0.5 will be considered a successful outcome.

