5.7 Administration of Procedural Intervention

Definity will be administered as an IV infusion via a peripheral vein (preferably the antecubital vein), with infusion rates of 4 to 10 ml/min (titrated to effect) through an 18 to 22 gauge angio-catheter.

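### The relatedness guidelines in 8.3.1 test only the study intervention, which the protocol describes as Definity, so harm from the research pressure needle can be coded Not Related and reported more slowly

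*Combined protocol and SAP*

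**What the plan says.** Section 8.3.1 begins broadly: "The relationship to study intervention or study participation must be assessed and documented for all adverse events". The next sentence names causes to weigh, and study procedures appear in the middle of the list: "Evaluation of relatedness must consider etiologies such as natural history of the underlying disease, concurrent illness, concomitant therapy, study-related procedures, accidents". The rules that follow are narrower: "The following guidelines are used to assess relationship of an event to study intervention". Under Related they include "The event reappears upon a re-challenge with the intervention". Under Not Related one of the two items is "An alternate etiology has been established".

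The protocol gives no formal definition of intervention, but its usage is consistent. The synopsis row describing the intervention covers baseline ultrasound, contrast infusion and 3D CEUS. Section 5.1 names Definity. Section 5.7, on the procedural intervention, deals only with the infusion: "Definity will be administered as an IV infusion via a peripheral vein". Section 5.8, on training, likewise covers only Definity.

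The pressure needle is described elsewhere. Section 1.4 calls interstitial fluid pressure (IFP) measurement one of the study's two parts. Section 1.4.1 says "The invasive pressure measurement procedure (with 18G needle) has low risk similar to a stereotactic breast biopsy" and lists bruising, swelling, infection and soreness. Section 6.3 requires one measurement in the tumor and one in the surrounding tissue.

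**The concern.** An investigator who sees a breast hematoma or infection plainly caused by the pressure needle has two readings available. Under the opening sentence of 8.3.1 the event is related to study participation. Under the guidelines the question is whether the intervention caused it. If intervention means Definity, the needle is a different, established cause, and the event fits Not Related.

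The Related items do little to correct this. Abatement on discontinuation and recurrence on re-challenge are drug criteria. They fit one completed infusion poorly and a completed needle pass not at all, and the section does not say whether every item must be met.

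The coding matters because relatedness sets some of the reporting deadlines in 8.4.1.2 and 8.4.2. The needle is used only for research, and every participant is exposed to it: 25 participants × 2 sites = 50 planned measurements. That figure is the exposure, not an estimate of how many events would be miscoded.

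**Working it through.** No sample-size or error-rate figure bears on this point. The check compares the deadlines for the same event coded Related and Not Related.

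**DSMC table, 8.4.2 (eight columns)**

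| Column | Related row | Unrelated row | Effect of coding Not Related |
|---|---|---|---|
| Grade 1 | quarterly | quarterly | none |
| Grade 2, unexpected | quarterly | quarterly | none |
| Grade 2, expected | quarterly | quarterly | none |
| Grade 3, unexpected, hospitalized | 48 h (death 24 h) | 5 working days | slower, still expedited |
| Grade 3, unexpected, not hospitalized | Phase I 48 h; Phase II 5 working days | quarterly | expedited review lost |
| Grade 3, expected, hospitalized | 48 h (death 24 h) | 5 working days | slower, still expedited |
| Grade 3, expected, not hospitalized | quarterly | quarterly | none |
| Grades 4 and 5 | 48 h (death 24 h) | Phase I 48 h (death 24 h); Phase II 5 working days | Phase I none; Phase II slower, still expedited |

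Count: 4 unchanged + 3 slower but expedited (one of them only under Phase II times) + 1 lost = 8. The synopsis labels the trial a pilot, so the documents do not say whether the Phase I or the Phase II times apply.

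**IRB, 8.4.1.2**

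- Grade 3-4, unexpected and at least possibly related to the study: 2 working days.
- Grade 3-4, unrelated to the study: 5 working days.
- The difference is 5 − 2 = 3 working days. This rule asks about relation to the study, not to the intervention, so the delay arises only if a needle injury is called unrelated to the study.
- Grade 3-4, expected and related: no explicit clock, so coding Not Related slows no stated deadline.
- Grade 5: 1 working day whatever the attribution.

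**Does a needle event reach 8.3.1 at all?**

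- 8.2 says subjects are monitored through the whole procedure and the 30-minute window, but it limits recording to the period from the start of Definity dosing to the end of its administration.
- 8.3 applies its documentation rules to the period set in 8.2.
- 6.3 orders the visit as infusion, wait for clearance, second data set, local anesthesia, then needle.

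Read literally, the recording period closes before the needle is used. Repairing 8.3.1 alone would therefore not ensure that needle harm is assessed.

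**The case against.** The strongest reply is that the governing sentence already covers the needle. Injury from a research-only procedure is plainly related to study participation, and the IRB rule speaks of the study, which Section 1.4 says includes the pressure measurement. This largely stands: the text permits a Not Related code but does not compel it. A reader might infer that the section classes study procedures as an alternative cause. It does not. It lists them as something to consider, and that phrase is its only explicit prompt to think of the needle.

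A second reply is that the consequences are limited, and this also stands. Section 8.4.2 sends all AEs to the DSMC whatever the attribution, and the halting rule in 8.5 has no relatedness test. The needle harms named in 1.4.1 would usually be expected under 8.3.2, which accepts the protocol as a source of risk information, and an expected Grade 3 event without hospitalization is reviewed quarterly in either row. Comparing contrast safety with needle safety is not a stated objective or planned analysis.

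A reader might also infer that the first Related item, that the event is known to occur, can never hold for an unexpected event, which would make related-and-unexpected reporting impossible. Section 8.3.2 rules that out, because a known event can be unexpected in severity or frequency.

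What these replies leave standing is that one section supports two readings, and for some events they lead to different deadlines.

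**Conclusion.** The point holds as an ambiguity that should be removed. The guidelines in 8.3.1 drop study participation and rely on a term that the protocol uses for Definity and its imaging, so needle harm can be coded Not Related.

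A reader might infer that expedited review is lost in general. The tables do not support that. It is lost in one of eight DSMC columns, slowed in three (for Grades 4 and 5 only under the Phase II times) and unchanged in four. The IRB delay of 3 working days applies only to unexpected Grade 3-4 events that are called unrelated to the study.

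The conclusion assumes that an investigator reads intervention as the synopsis and Section 5 use it, and that the event is recorded in the first place. The second assumption is itself uncertain, given the mismatch between 8.2 and 6.3. The documents give no basis for estimating how often miscoding would occur.

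**What to change.** 1. In 8.3.1, record two causality judgements for each AE: one for Definity/CEUS and one for the IFP procedure (local anesthesia plus needle). Count the event as study-related if either is at least possible.
2. Keep study procedures in the list of causes to consider, but state that harm from a research procedure is study-related and does not count as an alternate etiology.
3. State that the Related items are supportive and need not all be met, because de-challenge and re-challenge fit a single-visit exposure poorly.
4. Reconcile 8.2 and 8.3 with 6.3 so that events from the needle fall within the recording period and reach 8.3.1.
5. Align the wording of 8.4.1 and 8.4.2 with the new definition, and say which phase's times in the DSMC table apply to this pilot.

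The cost is one extra field on the AE form and some reworded paragraphs. The downside is small: some events due to the standard-of-care biopsy may be counted as study-related.

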8.3.2 Expectedness

The PI or Co-Investigator is responsible for determining whether an AE is expected or unexpected. An AE will be considered unexpected if the nature, severity, or frequency of the event is not consistent with the risk information previously described for the intervention. Risk information to assess expectedness can be obtained from preclinical studies, the investigator's brochure, published medical literature, the protocol, or the informed consent document.

8.3.3 Severity of Event

Adverse events will be graded for severity according to the Common Terminology Criteria for Adverse Events (CTCAE) version 5.0.

8.3.4 Intervention

Any intervention implemented to treat the adverse event must be documented for all adverse events.

8.4 Safety Reporting

8.4.1 Reporting to IRB

All incidents or events that meet criteria for unanticipated problems (UAPs) as defined in Section 8.1.1 Unanticipated Problems require the creation and completion of an unanticipated problem report form (OHR-20).

UAPs that pose risk to participants or others, and that are not AEs, will be submitted to the IRB on an OHR-20 form via the eazUP system within 5 working days of the investigator becoming aware of the event.

UAPs that do not pose risk to participants or others will be submitted to the IRB at the next continuing review.

8.4.1.1 Adverse Events

Grade 1 AEs will be reported to the IRB at continuing review.

Grade 2 AEs will be reported to the IRB at the time of continuing review.

8.4.1.2 Serious Adverse Events

SAEs will be reported to the IRB on OHR-10 forms via the electronic reporting system (eSAEy) according to the required time frames described below.

Grade 3-4 AEs that are unexpected and deemed to be at least possibly related to the study will be reported to the IRB within 2 working days of knowledge of the event.

Grade 3-4 AEs that are deemed unrelated to the study will be reported to the IRB within 5 working days.

Grade 5 AEs will be reported to the IRB within one working day of knowledge of the event.

All SAEs will be submitted to the IRB at continuing review, including those that were reported previously.

8.4.2 Reporting to SKCC DSMC

All AEs and SAEs, safety and toxicity data, and any corrective actions will be submitted to the DSMC per the frequency described in the SKCC DSMP. The report to the SKCC DSMC will also include any unanticipated problems that in the opinion of the PI should be reported to the DSMC.

For expedited reporting requirements, see table below:
DSMC AE/SAE Reporting Requirements

	Grade 1	Grade 2		Grade 3				Grades 4 and 5
	Unexpected and Expected	Unexpected	Expected	Unexpected		Expected		Unexpected and Expected
				With Hospitalization	Without Hospitalization	With Hospitalization	Without Hospitalization	
Unrelated Unlikely	Reviewed at Quarterly DSMC Meeting and IRB Annual Review	Reviewed at Quarterly DSMC Meeting and IRB Annual Review	Reviewed at Quarterly DSMC Meeting and IRB Annual Review	5 Working Days	Reviewed at Quarterly DSMC Meeting and IRB Annual Review	5 Working Days	Reviewed at Quarterly DSMC Meeting and IRB Annual Review	Phase I - 48 Hours (Death: 24 Hours) Phase II - 5 working days
Possible Probably Definite	Reviewed at Quarterly DSMC Meeting and IRB Annual Review	Reviewed at Quarterly DSMC Meeting and IRB Annual Review	Reviewed at Quarterly DSMC Meeting and IRB Annual Review	48 Hours (Death: 24 Hours)	Phase I - 48 Hours Phase II - 5 working days	48 Hours (Death: 24 Hours)	Reviewed at Quarterly DSMC Meeting and IRB Annual Review	Phase I and Phase II - 48 Hours (Death: 24 Hours)

8.4.3 Reporting to Funding Sponsor

Serious adverse events that occur with commercially available agents/devices are reported through Food and Drug Administration. The manufacturer (Lantheus) will also receive reports.

8.4.4 Reporting to FDA

The investigators will report in an IND safety report any suspected adverse reaction to study treatment (i.e., including active comparators) that is both serious and unexpected (21 CFR 312.32(c)(1)(i)) as soon as possible and no later than 7 days (for a death or life-threatening event) or 15 days (for all other SAEs) after the investigator's or institution's initial receipt of the information. Before submitting an IND safety report, the investigators needs to ensure that the event meets all three of the definitions:

- Suspected adverse reaction
- Serious
- Unexpected

SAEs will be reported on MedWatch Form 3500A, which can be accessed at:
<http://www.accessdata.fda.gov/scripts/medwatch/>.

MedWatch SAE forms will be sent to the FDA at:

MEDWATCH
[name]
[name]
Fax: [name] ([name])
<http://www.accessdata.fda.gov/scripts/medwatch/>

If the adverse event does not meet all three of the definitions, it will not be submitted as an IND safety report.

In addition, the investigators will identify in each IND safety report all IND safety reports previously submitted to FDA concerning a similar suspected adverse reaction and will analyze the significance of the suspected adverse reaction in light of previous, similar reports or any other relevant information (21 CFR 312.32(c)(1)). The analysis will include similar reports from all INDs held by the sponsor and any other relevant information known to the sponsor (21 CFR 312.32(c)(1)). Investigators will evaluate a suspected adverse reaction in the context of other related reports or adverse events, including those that occurred in the placebo or active comparator group and those that occurred in pre- and postmarketing studies.

8.4.5 Reporting of Pregnancy

If the subject is a woman of childbearing potential, she will have a urine pregnancy test prior to each CEUS study.

8.5 Halting Rules

Should the observed rate of AE/SAE at any of the scheduled interim analyses exceed 25%, study enrollment may be suspended so that the study committee may consider whether a change in protocol is necessary.

9 Study Oversight

In addition to the PI's responsibility for oversight, study oversight will be under the direction of the SKCC's Data and Safety Monitoring Committee (DSMC). The SKCC DSMC operates in compliance with a Data and Safety Monitoring Plan (DSMP) that is approved by the NCI.

10 Clinical Site Monitoring and Auditing

Clinical site monitoring and auditing is conducted to ensure that the rights of human participants are protected, that the study is implemented in accordance with the protocol and/or other operating procedures, and that the quality and integrity of study data and data collection methods are maintained. Monitoring and auditing for this study will be performed in accordance with the SKCC's Data and Safety Monitoring Plan (DSMP) developed by the SKCC Data and Safety Monitoring Committee (DSMC). The DSMP specifies the frequency of monitoring, monitoring procedures, the level of clinical site monitoring activities (e.g., the percentage of participant data to be reviewed), and the distribution of monitoring reports. Some monitoring activities may be performed remotely, while others will take place at the study site(s). Appropriate staff will conduct monitoring activities and provide reports of the findings and associated action items in accordance with the details described in the SKCC DSMP.

11 Statistical Considerations

11.1 Study Hypotheses

The main hypothesis is that the 3D subharmonic signals in the tumor and its surrounding tissue are correlated with the IFP values in them. The secondary hypothesis is that a marker from 3D subharmonic signals can predict the malignancy of breast tumor.

11.2 Analysis Plans

Radio frequency (RF) data from 3D SHAPE will be transferred to a PC for off-line analysis. 3D RF data from SHAPE will be composed of multiple 3D volumes (5 to 21 volumes) over time. Each 3D volume will consist of multiple 2D data sets (about 79 slices), which will be collected in the elevational direction. All data processing will be

performed using Matlab (R2015b; Mathworks, Natick, MA). Two regions of interest (ROI) will be selected in each elevational plane for SHAPE: one within the tumor and the other in the surrounding tissues (available top and/or bottom region of tumor). The ROIs of the tumor and surrounding area will be selected as a free form on the images generated from RF data (i.e., raw data before post-processing for on-screen display). The ROIs will be selected by the sonographer or radiologist. Then, a Fast Fourier Transform will be computed for each A-line within the ROI to obtain the frequency spectrum. The maximum magnitude from the resultant frequency spectrum will be extracted from each pre- and during infusion data sets and the ratio will be calculated for each ROI. If both top and bottom regions are selected as a surrounding area ROI, then the ratios will be averaged to one value. Finally, the obtained subharmonic signal ratios from the tumor and the surrounding area will be compared to the direct IFP measurements. Pearson's correlation coefficients will be computed between SHAPE results and direct IFP measurements by Stryker compartment pressure monitoring system. These data will also be rigorously analyzed for agreement using Bland-Altman analysis (Bland & Altman, 1999) among tumor and healthy tissue samples. To explore if the relationship between SHAPE results and IFP is confounded by or might depend on study variables collected (e.g.'s, patient characteristics, tissue/tumor characteristics, etc.) linear mixed effects or generalized estimating equations modeling will be used. Generalized linear mixed logistic or GEE logistic modeling of tumor vs. non-tumor samples will be used to explore the potential for using SHAPE results as a novel functional predictor of breast tumor malignancy. Additionally, the subharmonic signal ratio from the tumor will be used to predict the malignancy of breast tumor using a biopsy result as a gold standard. The Mann-Whitney or Student's t-test will be performed depending on the distribution of the results.

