Participant Participation Duration: The participation duration is about 80-90 minutes (including 30 minute-long monitoring time) in a single visit.

Estimated Time to Complete Enrollment: 15 months

Schematic of Study Design:

Prior to
Enrollment

Total 25: Obtain informed consent. Screen potential subjects by inclusion and exclusion criteria; obtain history, document.

Visit 1
On the day
Of a Biopsy

Conventional ultrasound imaging will be performed to examine the tumor followed by CEUS exam. Before collecting CEUS data, Definity will be administered IV and the acoustic settings will be optimized using a built-in software in a modified Logiq E9 or E10 scanner. The 3D SHAPE data will be collected using the determined acoustic settings during the infusion. Then, we wait for the clearance of Definity and another set of SHAPE data will be collected without Definity keeping the same acoustic settings.

The subject will have local anesthesia procedure and IFP will be measured from the breast tumor and its surrounding tissue using an 18G single-use needle connected to Stryker pressure monitoring system. The measurement procedure will be guided by ultrasound imaging. The measurements will be documented as well as their locations.

Compare the results from 3D
SHAPE data to IFP measurements
and find the correlation

1 Introduction

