6.3 Treatment Period

On the visit day

- Perform Baseline Ultrasound imaging.
- Administer Definity (IV infusion)
 - Determine the optimized acoustic settings for 3D SHAPE imaging
 - Perform CEUS exam and collect 3D SHAPE data

- Wait for clearance of Definity
 - Collect 3D SHAPE data
- Local anesthesia procedures will be performed using simple Lidocaine 1%, or combined with 1:100,000 Epinephrine (EPI) before the IFP measurements.
- Take a single IFP measurement each from the breast tumor and its surrounding tissue using Stryker compartment pressure monitoring system with ultrasound imaging guide

Participants will be monitored for 30 minute following the administration of Definity.

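### The surrounding-tissue SHAPE region is not tied to the side of the tumor where the pressure was read, so a compliant pair can compare different tissue

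*Combined protocol and SAP*

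**What the plan says.** **SHAPE side (section 11.2).** The data are three-dimensional: "Each 3D volume will consist of multiple 2D data sets (about 79 slices" in the elevational direction. In each plane two ROIs are drawn: "one within the tumor and the other in the surrounding tissues (available top and/or bottom region of tumor". They are drawn by hand: "The ROIs of the tumor and surrounding area will be selected as a free form on the images generated from RF data", and "The ROIs will be selected by the sonographer or radiologist". For surrounding tissue, "If both top and bottom regions are selected as a surrounding area ROI, then the ratios will be averaged to one value".

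**Pressure side (section 6.3 and the Schematic of Study Design).** The instruction is "Take a single IFP measurement each from the breast tumor and its surrounding tissue", under ultrasound guidance. The schematic adds that this is done "using an 18G single-use needle connected to Stryker pressure monitoring system". Nothing says whether the surrounding-tissue reading lies above, below or beside the tumor, or how far from it.

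**The link between them.** The schematic states: "The measurements will be documented as well as their locations". Section 6.3 does not repeat this, the data list in 15.3 names the pressure measurements but not their positions, and 11.2 compares the ROI ratios with the readings without referring to location.

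**What rests on the pairing.** Section 2.2.1 counts a Pearson correlation above 0.5 as success. Section 11.3 sizes the study for a correlation of 0.5 to 0.6 and chooses 25 patients.

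**The concern.** The primary comparison pairs an imaging value with a pressure value and asks whether they move together. That is cleanest when both describe the same tissue. For surrounding tissue, the plan fixes neither end. The ROI goes wherever tissue above or below the tumor is available, and the needle goes wherever the operator takes the reading. If pressure or perfusion differs around the tumor, the difference enters each pair as error that has nothing to do with whether SHAPE senses pressure.

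Two things are at stake. The chance of meeting the success criterion falls. A disappointing result also becomes hard to read, because a poor sensor and a good sensor compared with the wrong tissue would look alike. The reading is invasive and taken once, so its position cannot be changed afterwards.

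**Working it through.** **1. The plan's own figure.** Inputs from section 11.3: two-sided 5% level, 80% power, correlation 0.5 to 0.6. By Fisher's z, n = ((1.960 + 0.842) / atanh(r))² + 3.
- r = 0.5: atanh = 0.549, n = 29.0.
- r = 0.6: atanh = 0.693, n = 19.3.

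Exact bivariate-normal calculation gives 29 and 19, so the stated 19 to 29 is reproduced. At the chosen n = 25, exact power is 74.9% at r = 0.5 and 91.3% at r = 0.6. The sample-size section contains no explicit allowance for mismatch.

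**2. Which pairs the protocol permits.**

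| SHAPE region (11.2) | Pressure reading (6.3) | Compliant? | Same side? |
|---|---|---|---|
| Top only | Above tumor | Yes | Yes |
| Top only | Below tumor | Yes | No |
| Top only | Beside tumor | Yes | No |
| Top and bottom, averaged | Above or below | Yes | Half |
| Top and bottom, averaged | Beside tumor | Yes | No |

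Bottom-only cases mirror the top-only rows. For the tumor pair, the ROI and the needle both lie in one ultrasound-identified mass. What remains there is variation within the mass. Section 4.1.1 sets a minimum size of 1 cm and no maximum.

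**3. Direction of the effect.** Let m be the correlation between pressure where SHAPE was sampled and pressure where the needle was. If the location error is unrelated to the true values, the population correlation becomes approximately r × m. The documents give no figure for m, so these values are assumptions: 0.60 × 0.9 = 0.54 and 0.60 × 0.8 = 0.48.

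**4. Effect on the success criterion.** The criterion is judged on the sample correlation. For n = 25 independent bivariate-normal pairs, P(sample r > 0.5) ≈ Φ(√22 × [atanh(ρ) + ρ/48 − atanh(0.5)]), where ρ/48 is the small-sample bias term ρ/(2(n − 1)).

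| Population ρ | atanh(ρ) + ρ/48 | minus 0.5493 | × √22 (4.690) | P(r > 0.5) |
|---|---|---|---|---|
| 0.60 | 0.7056 | 0.1563 | 0.733 | 77% |
| 0.54 | 0.6154 | 0.0661 | 0.310 | 62% |
| 0.48 | 0.5330 | −0.0163 | −0.077 | 47% |

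Simulation gives the same three percentages. The correlation is taken as a magnitude, since section 1.2 describes an inverse relation. The 25 pairs stand for a correlation within surrounding tissue, one pair per patient.

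**The case against.** **The objective is at the level of the region, not the point.** Sections 2.1.1 and 11.1 speak of pressure in the tumor and in its surrounding tissue, and the Study Summary treats these as the two sites. A whole-tumor SHAPE value answers that question. This stands. A reader might infer that the whole-tumor ROI is an error and that a needle-centred ROI should replace it, but the documents do not support that.

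**The planned correlation may already include mismatch.** Section 11.3 describes 0.5 to 0.6 as the correlation between SHAPE and the direct readings, which is an observable quantity. Multiplying it by m may count the same error twice. This stands too, which is why step 4 is an illustration and not a forecast.

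**Pooling may hide the loss.** Section 1.1 cites a mean of 29 mmHg in invasive ductal carcinoma against −0.3 to 3.6 mmHg in normal and other tissue. Suppose tumor and surrounding sites are pooled, half the tumors are invasive (a quarter of all sites), and the means are 29 and 2 mmHg. The between-group SD is then 27 × √(0.25 × 0.75) = 11.7 mmHg. Mismatch SDs of 3, 5, 8 and 10 mmHg give m = 11.7/√(11.7² + SD²) of about 0.97, 0.92, 0.83 and 0.76. A low m would need a large local difference, which the documents do not show. But the plan does not say whether sites are pooled. A pooled correlation would also partly reflect tissue type, and this contrast does nothing for a correlation within surrounding tissue.

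**Exact co-location is not simple wording.** Under 6.3 the SHAPE data are acquired before the needle is placed, so the needle is not in the volumes, and no registration to the planes is described. A small ROI in the wrong place could match worse than the regional average. This argues against making a needle-local ROI primary. It does not argue against matching the side, which needs only a coarse location.

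**Conclusion.** The point holds for surrounding tissue. The protocol lets the SHAPE region and the pressure reading fall on different sides of the tumor, and 11.2 leaves unused the location that would prevent it. The effect is likely to be attenuation, provided that the location error is unrelated to the true values. The size cannot be derived from the documents. With 25 pairs, a fall in population correlation from 0.60 to 0.54 or 0.48 would lower the chance of meeting the criterion from about 77% to 62% or 47%. The tumor pair is affected less.

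A reader might go further and infer that the trial falls under its own threshold once m drops below 0.5/0.6 = 0.83, or 0.5/0.7 = 0.71. That is not supported. The factor m is assumed, a true correlation of 0.7 appears nowhere in the documents, and 0.6 may already be the observable value. The criterion also applies to the sample correlation, so the chance of success declines gradually with no cut-off. Nor do the documents show that mismatch will occur in any given patient, only that nothing prevents it. For a 25-patient pilot this is an inexpensive improvement, not a flaw that invalidates the design.

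**What to change.** **Section 6.3.** Take the surrounding-tissue reading within the imaged 3D volume, in a region above or below the tumor that can serve as the ROI. Record side, depth and approximate elevational plane for both readings, and add these items to the data list in 15.3.

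**Section 11.2.**
- For the pressure correlation, use the surrounding-tissue ROI on the same side as the documented reading. Keep the top-and-bottom average as a secondary analysis only.
- Give the person drawing the ROI the location but not the pressure value.
- Keep the whole-tumor ROI as primary for the tumor pair.
- Add, for both sites, a sensitivity analysis with an ROI local to the documented needle position and a radius fixed in advance.

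**Cost.** A little more recording at the visit and more off-line processing. The local ROI will have a noisier spectrum and depends on approximate registration, which is why it stays a sensitivity analysis. The sample-size formula need not change. The 6.3 change has to be in place before readings are taken.
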